2 PARTICIPANTS

2.1) **Participants**. Describe the general characteristics of the subject populations or groups, including age range, gender, health status, and any other relevant characteristics.

Review the HSD website for current quidelines about which in-person research activities are allowable.

Up to 20 nurses will be recruited from Harborview Medical Center acute care units serving patients admitted for medical, surgical, or traumatic injury reasons.

- 2.2)Inclusion and exclusion criteria.
 - **a. Inclusion criteria.** Describe the specific criteria that will be used to decide who will be included in the research from among interested or potential subjects. Define any technical terms in lay language.

Nurses working on acute care units at HMC.

b. Exclusion criteria. Describe the specific criteria that will be used to decide who will be excluded from the research from subjects who meet the inclusion criteria listed above. Define any technical terms in lay language.

Nurses unable to complete research activities remotely will be excluded. Remote training and research activities require the use of laptop, computer, or smart phone with internet access.

2.3 Prisoners. IRB approval is required in order to include prisoners in research, even when prisoners are not an intended target population.

Is the research likely to have subjects who become prisoners while participating in the study?

For example, a longitudinal study of youth with drug problems is likely to have subjects who will be prisoners at some point during the study.

Yes → If yes, if a subject becomes a prisoner while participating in the study, will any study procedures and/or data collection related to the subject be continued while the subject is a prisoner?

No
Yes → If yes, describe the procedures and/or data collection that will continue with prisoner subjects

2.4 Will the proposed research recruit or obtain data from individuals that are known to be prisoners?

For records reviews: if the records do not indicate prisoner status and prisoners are not a target population, select "No". See the GUIDANCE Prisoners for the definition of "prisoner", which is not necessarily tied to the type of facility in which a person is residing.

X No
Yes → If yes, answer the following questions (i – iv).

i. Describe the type of prisoners, and their location(s):

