	sonnel. For MRI scans that will be conducted at the DISC, CHN or BMIC research facilit cate who will be responsible for operating the MRI scanner by checking all that apply. MRI technician who is formally qualified

h MRI facility At which facility(ies) will the MRI scans occur? Check all that apply

5.4 Data variables. Describe the specific data that will be obtained (including a description of the most sensitive items). Alternatively, a list of the data variables may be uploaded to **Zipline**.

Measures & Variables

Nurse training and technology acceptability will be assessed using the System Usability Scale (SUS), openended questions, and a modified version of the Client Satisfaction Questionnaire-8 (CSQ-8) to assess nurse satisfaction with the training.

Nurses will complete demographic questions (e.g., gender, race/ethnicity, age) and asked about their length of current employment, training background, and experience with suicide prevention and other behavioral interventions.

Nurse training targets will include use of the technology and nurse motivation for training and delivery of safety planning. Self-report surveys at post-training and the 6-month follow-up will include questions to assess whether and when nurses used the Client Bot and Lyssn feedback system and how they used it in their training and practice. Use data will also be collected by Client Bot and Lyssn systems, which will consist of how often nurses accessed the program, times of day of use, how long nurses spent on the program, and features used. A measure of nurse motivation to use the training materials, including the technology, will be asked at each survey time point. This will include variables such as nurse interest in the material, technology, and willingness to persist when challenged by practicing skills and getting corrective feedback. Motivation to use the general counseling skills to conduct collaborative safety planning with patients (i.e., transfer of training) will be assessed by adapting measures from the Theoretical Domains Framework (TDF; e.g., beliefs about capabilities and consequences, behavioral intentions, negative emotions).

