For example: Consultation with publications about research subjects' preferences, disease-focused nonprofit groups, patient interest groups, or other researchers/study staff with experience with the specific population. It may also involve directly consulting selected members of the study population.

I have experience conducting research with nurses providing services to hospitalized patients at Harborview and at hospitals in Washington and other U.S. states. This research includes training nurses in brief behavioral health interventions and asking them to complete research surveys and standardized patient role-plays.

f. Ongoing process. For research that involves multiple or continued interaction with subjects over time, describe the opportunities (if any) that will be given to subjects to ask questions or to change their minds about participating.

The study includes training and research activities that occur over multiple occasions. Some activities are scheduled with the research team, such as the standardized patient role-plays. Nurses will be reminded that they may opt out of participating at any point. They will be encouraged to contact the PI or research team by phone or email anytime with questions or concerns or to stop participating. Nurses will be reminded that there is no consequence for withdrawing their participation and they will receive remuneration for attempted activities (e.g. they will receive remuneration for partially-completed surveys).

8.3 Electronic presentation of consent information. Will any part of the consent-related information be provided electronically for some or all of the subjects?

This refers to the use of electronic systems and processes instead of (or in addition to) a paper consent form. For example, an emailed consent form, a passive or an interactive website, graphics, audio, video podcasts. See GUIDANCE Electronic Informed Consent for information about electronic consent requirements at UW.

X

No \rightarrow If no, skip to question 8.4

'es → If yes, answer questions a through e

a. Describe the electronic consent methodology and the information that will be provided.

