Observation/assessment burden. To manage potential performance anxiety related to the standardized patient role-plays, nurses will be reminded that the assessments will be used only for the research study and will not be shared with their supervisor or others who may use the information in an evaluative way. We will remind nurse participants that the purpose of our project is to develop effective training methods, not to evaluate them as professional nurse providers. Nurses will be reminded that all activities are voluntary, including the training activities. They will be allowed to quit using any of the training technology, end the session with the standardized patient, skip survey questions, and leave the focus group early or not answer questions if they choose. Nurses will have an opportunity to debrief with the research staff after the standardized patient. Nurses will be able to schedule the standardized patient to occur at their convenience.

Distress related to talking about suicide. Nurses will be allowed to end specific training or research activities if feeling distressed. The PI will be available to debrief nurses' experiences with training and research activities and nurses may reach the PI at her cell phone during the workday or the PI will return calls the following day. The PI will routinely reach out to nurses enrolled in the study and check in about their experience. The PI is a licensed clinical psychologist who routinely supervises and consults with mental health providers on managing distress associated with patient care. [name] has expertise in suicide prevention trials and training clinicians in suicide prevention and treatment and will also be available to consult with the PI on these issues.

Coercion. Nurses will be recruited by the PI/research team. The PI/research team will post advertisements, attend staff meetings, ask the unit nurse manager to send out a recruitment email, or email potential nurse participants directly to invite them to participate in the study. Nurses will be reminded that they can opt out of any part of the training and research activities and that whether they complete the activities is documented for research purposes and not reported to fellow nurses or supervisors. Remuneration was designed to balance adequate compensation for time and effort without being too large of an amount to be coercive.

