Nurses will be recruited on an ongoing basis, which is expected to take about two months. Nurses will engage in 3-4 hours of training that is expected to take about one month to complete. Enrolled nurses will also engage in evaluation activities that will take 3 hours total. In the first month, this includes several standardized patient role-plays of suicide safety planning and survey measures. Six months after the training is completed, nurses will be asked to complete a 6-month standardized patient role-play, 6-month follow-up survey, and participate in an end-of-study 1-hour focus group. Some role-plays will serve dual purposes as part of the training as well as to collect training outcome data.

Primary Outcomes

Acceptability. Nurse training and technology acceptability will be assessed using the System Usability Scale (SUS), open-ended questions, and a modified version of the Client Satisfaction Questionnaire-8 (CSQ-8) to assess nurse satisfaction with the training.

Training outcomes. Nurse training outcomes of general counseling skill quality and quality of safety planning will be assessed using standardized patient assessments. Nurses will complete four 30-minute role-plays over the course of the evaluation. These will be conducted by research staff or paid actors via Zoom, recorded, and assessed for general counseling skill quality using the Lyssn system. Pre- and post-training and follow-up role-plays will be assessed for fidelity to the safety planning intervention by the PI. Self-reported perception of skills will be assessed via survey at baseline, post-training and 6-months post-training using methods modified from training clinicians in evidence-based psychotherapy.

Secondary Outcomes

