Quantitative data will be viewed graphically and analyzed descriptively. Qualitative open-ended responses to questions will be summarized into common themes or content analyzed, as appropriate. Acceptability of the training will be supported by scores above 24 (indicates average of 3) on the CSQ-8 provider-version, above 67 on the SUS, and responses to open-ended questions based on relevant TDF constructs. Feasibility of the training will be supported by nurse use statistics collected by the computer technology and completion of all training parts (web-based didactic, Client Bot, and Lyssn feedback). Focus group qualitative data will be content analyzed according to TDF constructs.

3. Human Subjects Considerations

Inclusion/exclusion Criteria

All nurses working on participating units will be eligible for participation. There are no exclusion criteria. Nurses will opt into the study based on interest and willingness, including willingness to utilize a computer and the internet to participate in the web-based training activities.

Informed Consent

Informed consent may occur in person, by phone, or by videoconference. The PI/research staff will send the informed consent document to nurses ahead of time and then meet to go over and explain the study, review the consent form, and answer any questions. We will obtain a waiver of documentation of informed consent to facilitate virtual consent procedures. Nurses are expected to be literate in English at the high school level. They are also expected to be able to use computer, internet, REDCap technology as they routinely use these or similar systems in their routine work.

Risks Associated with Study Participation

Confidentiality. Nurses may be concerned that performance on the standard patient role-plays and responses to study surveys and focus group questions may be shared with colleagues or supervisors. **Observation/assessment burden.** Completing training and research tasks may be perceived as burdensome and nurses may experience some performance-related anxiety on the standardized patients. Nurses may experience some frustration interacting with the technology, which may depend on nurse computer technology literacy.

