- a) Standardized patient role-play recordings Standardized patient role-play scenarios will be developed by the research team for the purposes of the study. The PI will train research staff/standardized patient actors, in the scenarios. The PI will review standardized patient role-plays and provide feedback and retraining to staff/actors as needed. Research staff will test audio/video recording equipment prior to use. Audio/video recordings will be checked immediately following the role-play session for recording quality and any problems addressed prior to the next session. The PI has been trained in coding of suicide safety planning for quality and will ensure accurate downloading of Lyssn data and entry of quality assessment data.
- b) REDCap surveys All REDCap data collection surveys will be pilot tested by the research team. The surveys will be designed to reduce potential for human error in data entry or unintentionally skipping items. The PI and/or research staff will periodically review the survey data to ensure the tools are functioning properly.
- c) Focus group recordings & transcripts
 Research staff will test audio/video recording equipment prior to use. Audio/video recordings
 will be checked immediately following the focus group for recording quality and any problems
 addressed prior to the next session. The PI will review transcripts to ensure their quality.
- d) Technology use data

 The PI will work with technology consultants to ensure the technologies are accurately capturing usability data. The PI will ensure the data is transferred properly to the research team and is prepared appropriately for analysis. The PI and/or research staff will periodically review the technology use data captured to ensure the tools are functioning properly.

5. Event Reporting

The study team will follow procedures for reporting reportable events required of both the UW IRB (Guide to Reporting New Information - UW Research (washington.edu)) as well as NIMH (NIMH Reportable Events Policy).

The following Office of Human Research Protection (OHRP) Definitions will be used to meet reporting requirements:

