Statistical Analysis Plan for eLearning for Suicide Prevention, ID: STUDY00013577, NCT05178121

We will examine descriptive statistics for all outcomes, including frequencies for categorical variables and the mean, standard deviation, and confidence intervals based on the standard error of the mean for variables observed across timepoints.

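### Do the acceptability cut-offs count a skipped item as dissatisfaction, and does a cut-off above 24 contradict its own gloss?

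*Combined protocol and SAP*

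**What the plan says.** The Data and Safety Monitoring Protocol (DSMP), section 2, lists acceptability among the primary outcomes. It is measured with the SUS, open-ended questions and "a modified version of the Client Satisfaction Questionnaire-8 (CSQ-8"). Under Plan of Analysis in the same section, support for acceptability is defined by "scores above 24 (indicates average of 3) on the CSQ-8 provider-version, above 67 on the SUS", read alongside the open-ended answers.

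Incomplete forms are allowed. Protocol section 10.1 lets nurses "skip survey questions, and leave the focus group early or not answer questions if they choose", and section 8.2(f), on ongoing consent, says "they will receive remuneration for partially-completed surveys". On the other side, DSMP section 4 (Data Integrity) says: "The surveys will be designed to reduce potential for human error in data entry or unintentionally skipping items".

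The SAP is descriptive: "We will examine descriptive statistics for all outcomes, including frequencies for categorical variables and the mean, standard deviation, and confidence intervals". Protocol section 2.1 sets the size: "Up to 20 nurses will be recruited from Harborview Medical Center acute care units".

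The documents do not say how either scale is scored when an item is blank. They do not give the item count or response range of the modified CSQ-8. They do not say whether the cut-offs are read for each nurse or against the group mean.

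**The concern.** A cut-off of 24 matches an item average of 3 only if eight items are answered. Nurses may leave items blank and are still paid, so some totals could rest on fewer items. A plain sum falls with every blank, however satisfied the nurse is. The SUS total would behave the same way.

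There is also a wording tension. A nurse who answers 3 throughout scores exactly 24, which is not above 24, although the parenthesis ties 24 to an average of 3.

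These are the only numeric success criteria in the plan, and they belong to a primary outcome whose findings feed revision of the training and a larger trial. If an artefact of blanks made the training look unacceptable, it could be revised for the wrong reason.

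**Working it through.** **Inputs.** From the DSMP Plan of Analysis: CSQ-8 above 24, said to indicate an average of 3; SUS above 67. From protocol section 2.1: at most 20 nurses. Assumed, because the documents do not state them: eight CSQ-8 items scored 1 to 4, and a SUS of ten items each worth 0 to 10 points. The zero for a blank in steps 3 to 5 is also an assumption, used to find the worst case.

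**1. The plan's own figure.** 24 / 8 = 3.00. The gloss is correct, and it implies that the modified scale keeps eight items.

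**2. The strict inequality.** 24 > 24 is false. For a complete form, the lowest passing total is 25, a mean of 25/8 = 3.125. Read for each nurse, the bar sits one point above straight 3s. Read against a group mean, exactly 24.0 is an edge case.

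**3. Blanks summed as zero, one nurse, CSQ-8.** With *k* blanks, the answered items must average above 24 / (8 − *k*):
- *k* = 1: 24/7 = 3.43. A nurse giving only 3s totals 21.
- *k* = 2: 24/6 = 4.00. The maximum is 6 × 4 = 24, so the cut-off cannot be exceeded.

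**4. Blanks summed as zero, one nurse, SUS.** At 7.5 points per item: 10 × 7.5 = 75 complete, 9 × 7.5 = 67.5 with one blank (still above 67), 8 × 7.5 = 60 with two.

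**5. Blanks summed as zero, group mean, CSQ-8.** Let a proportion *p* of nurses skip one item each, and let the true item mean be *m*. The group mean is 8*m* − *mp*, which falls below 24 when *p* > 8 − 24/*m*.
- *m* = 3.1: the group mean is 24.8 − 3.1*p*, giving 24.49 at 10%, 24.18 at 20% and 23.87 at 30%. The crossing is at 0.8/3.1 = 0.258. With 20 nurses, five skippers (25%) leave 24.8 − 0.775 = 24.03; six (30%) give 23.87.
- *m* = 3.125: the crossing is at 8 − 7.68 = 0.32.
- *m* = 24/7 = 3.43: the crossing is at 8 − 7 = 1, so even one blank from every nurse brings the mean only to 24.

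The verdict therefore flips only when satisfaction is already close to the bar and a sizeable share of nurses skip. The documents give no skip rate.

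**6. The same form under other scoring.** A nurse answers 3 on seven items and leaves one blank. The mean of answered items is 21/7 = 3.00, and the prorated total is 21 × 8/7 = 24, the same as a complete form of straight 3s. Complete-case scoring leaves the form out. None of the three penalises a blank as such.

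**7. Which rule does the text impose?** None. The parenthesis expresses the cut-off as an item average, which points towards averaging answered items more than towards adding zeros.

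**The case for a change.** The best case for a change starts from the silence. Acceptability is a primary outcome, deliberate skipping is explicitly protected, and the survey-design safeguard addresses only accidental omissions. Without a stated rule, the same data could pass or fail according to a choice made after they are seen. A descriptive mean still needs a scoring rule. Complete-case scoring, though free of the zero-score penalty, would drop nurses from a sample of at most 20. Closing the gap would cost a sentence or two and no new data.

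Some of this stands. The scoring rule and the unit of the cut-off are unstated, and under a per-nurse reading straight 3s do not clear the bar.

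The rest is weaker. Permission to skip and payment for attempted surveys are participant protections; they do not show that blanks will be common. The plan also has survey data reviewed periodically, and in a file this small any blank is easy to see. The criteria are worded as support, are read with open-ended responses, and trigger no test or go/no-go decision; focus groups and technology-use data also inform the evaluation. Moving the bar to at least 3.0 would lower it by preference and correct no arithmetic error.

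**Conclusion.** The concern does not call for a change. Its harmful form needs blanks to be scored as zero, and the documents do not say that. Under that worst case, with items assumed to run 1 to 4, a nurse with one blank must average above 3.43 on the rest. At an assumed item mean of 3.1, the group mean drops below 24 once more than about 26% of nurses skip an item, which is six of 20. Under item means or proration the penalty disappears.

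The strict cut-off and its gloss are compatible: the parenthesis says what 24 corresponds to, and the criterion asks for more than that. What is left is a missing scoring detail in a descriptive pilot of at most 20 nurses, with accidental skips limited by design and other evidence read beside the scores. An analyst would ordinarily average or prorate the answered items and report having done so.

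This conclusion rests on the assumed item formats and on blanks being infrequent, which the documents neither confirm nor contradict.
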